10.6 Pregnancy

All pregnancies and outcomes of pregnancy will be reported to the sponsor and AstraZeneca, after obtaining separate consent from the study participant/participant partner. If a patient becomes pregnant during the course of the study IP should be discontinued immediately. Pregnancy itself is not regarded as an AE unless there is a suspicion that the IP under study may have interfered with the effectiveness of a contraceptive medication. Congenital abnormalities/birth defects and spontaneous miscarriages should be reported and handled as SAEs. Elective abortions without complications should not be handled as AEs. The outcome of all pregnancies (spontaneous miscarriage, elective termination, ectopic pregnancy) should be reported. If any pregnancy occurs in the course of the study, then the Investigator or other site personnel informs the sponsor's representatives within 1 day of when he/she became aware of it.

10.7 Overdose

Dapagliflozin has been well tolerated at doses of up to 500 mg/day in single dose testing in healthy volunteers and up to 100 mg/day in repeat dose testing for 14 days in healthy volunteers and patients with T2D. Overdose defined as at least twice the intended dose within the therapeutic interval, whether accidental or intentional, suspected by the Investigator or spontaneously notified by the patient, will be recorded in the eCRF overdose module. If the overdose is symptomatic, it will also be recorded as an adverse event. If an overdose is suspected, monitoring of vital functions as well as treatment should be performed as appropriate.

An overdose with associated AEs is recorded as the AE diagnosis/symptoms on the relevant AE modules in the eCRF and on the Overdose eCRF module. An overdose without associated symptoms is only reported on the Overdose eCRF module.

10.8 Annual safety report

In addition to the expedited reporting of SUSARs, the sponsor will submit, once a year throughout the clinical trial, a safety report to the accredited METC, competent authority, and competent authorities of the concerned Member States. This safety report consists of:

• a list of all suspected (unexpected or expected) adverse reactions and serious adverse reactions, along with an aggregated summary table of all reported serious adverse reactions, ordered by organ system, per study;

• a report concerning the safety of the subjects, consisting of a complete safety analysis and an evaluation of the balance between the efficacy and the harmfulness of the medicine under investigation. All safety reports should be simultaneously communicated to Astra Zeneca.

11. STATISTICAL ANALYSIS

The analytical plan mirrors that operationalized in previous work^{92, 93}. Data will be analyzed using Stata/SE 15. The primary outcome is the difference in blood pressure reduction in dapagliflozin vs. placebo treated participants at 12 weeks. Secondary outcomes will consist of within and between group changes metabolic, vascular, renal and transplant outcomes. Frequency of adverse events, non-adherence and drug discontinuation will be tabulated (no comparisons will be made). Within group comparisons will be analyzed using repeated measures ANOVA (baseline value will be included in these ANOVA models). As in previous work, between group comparisons will also be made using a 2-way ANOVA with treatment as the dependent variable^{71, 92, 94-96}. This clinical trial is not sufficiently powered to detect sex- or gender-based differences. However, data analyses will be stratified by sex and gender to detect any similarities or differences. These will be exploratory analyses and hypothesis generating, which may be informative in the design of future studies. Other exploratory analyses will include stratification by GFR (measured iohexol GFR of <45 ml/min/1.73m² vs. >45 ml/min/1.73m²), as well as diabetes type (T2D and PTDM). An intention-to-treat (ITT) approach will be used. Adherence will be measured (see '**Randomization**' in the proposal), and non-adherent patients will also be included in the ITT analysis.

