# 1. Analysis for the primary objective:

- 1.1. To assess dapagliflozin-related acute and chronic changes in the primary outcome of seated systolic blood pressure compared to placebo, linear mixed-effects models will be used. Two separate models will be fit. For acute change, the vector of outcomes will include the baseline and 1-week values (i.e. Visit 3 and Visit 4 values). For chronic changes, the vector of outcomes will include the baseline and 12-week values (i.e. Visit 3 and Visit 9 values). The covariates will include the visit and treatment-by-visit interaction; due to randomization, a covariate for the main effect of treatment will not be included. The treatment-by-time coefficient, its 95% confidence interval, and its p-value will be used to assess the effect of treatment.
- 1.2. We will repeat this analysis with:
  - a. Seated diastolic blood pressure as an outcome
  - b. Seated mean arterial pressure as an outcome

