#### 5. Pre-specified post-hoc analyses:

- 5.1. The same models described in the analysis of primary objective 1.1 will be performed for the outcome.
- 5.2. The same models described in the analysis of exploratory objective 3.2 will be completed for each of the different outcomes.

Analysis population: The intention to treat population will be used for all analyses.

*Hypothesis testing:* For hypothesis testing, a 5% significance level will be used (two-sided). No interim analyses will be performed. For secondary objectives, nominal p-values will be reported.

*General model assumptions and model diagnostic procedures:* For the linear mixed-effects models with visit and treatment-by-visit interaction as covariates, a participant-level random intercept will be included. Restricted-maximum-likelihood will be used for estimation and the missing-at-random framework will be assumed. Plots of marginal and conditional residuals will be used for model diagnostics and assessment. Similar diagnostic procedures will be used for the linear regression models.

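### Protocol section 11 and the SAP give different between-arm analyses for the primary SBP comparison, and the protocol's, read literally, cannot estimate the week-12 difference

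*Protocol*

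**What the plan says.** Protocol section 11 states: "The primary outcome is the difference in blood pressure reduction in dapagliflozin vs. placebo treated participants at 12 weeks". Two analysis sentences follow. The first is "Within group comparisons will be analyzed using repeated measures ANOVA", with the baseline value included in those models. The second is "between group comparisons will also be made using a 2-way ANOVA with treatment as the dependent variable". This is the only between-arm method in the protocol. Section 11 does not name the second ANOVA factor, say whether the response is the visit value or the change, mention a participant term, or give a missing-data rule. It does specify an intention-to-treat approach.

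SAP 1.1 says that for change "in the primary outcome of seated systolic blood pressure compared to placebo, linear mixed-effects models will be used". There are two models, one for baseline and week 1 and one for baseline and week 12. Each contains visit and treatment-by-visit, and "due to randomization, a covariate for the main effect of treatment will not be included". The treatment-by-visit coefficient, with its 95% CI and p-value, is the test of the drug. The closing paragraphs of the SAP add a participant random intercept and REML, and "the missing-at-random framework will be assumed".

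The SAP contains no ANOVA and no within-arm test. The protocol contains no mixed model.

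**The concern.** The rule for the primary comparison is wrong as written in one document and replaced without comment in the other. Protocol section 12.1 commits the trial to compliance with the protocol, so the ANOVA sentence cannot be assumed to have lapsed. While both texts stand, the analysis of the primary endpoint could be chosen after the data are seen, and the candidate analyses can disagree on significance.

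A second issue sits beside it. Section 11 lists within-group changes among the secondary outcomes and tests them. A significant fall in one arm and a non-significant fall in the other is easily read as a drug effect, although neither test compares the arms.

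**Working it through.** **Inputs.** From protocol section 5.3: effect 6.5 mmHg, SD 8 mmHg (taken as the SD of change), two-sided alpha 0.05, 80% power, 24 per arm, 10% attrition, final 52. The baseline to week-12 SBP correlation (rho) is not given, so 0.3 to 0.8 is assumed, with equal variance at both visits.

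**1. The plan's own figure.** n per arm = 2 × (1.96 + 0.84)² × 8² / 6.5² = 23.8, so 24, or 48 in total. This reproduces the protocol. Power at 24 per arm is 80.4% by the normal approximation and 78.7% by noncentral t. Inflating for attrition gives 48/0.9 = 53.3 or 48 × 1.1 = 52.8, against the stated 52, a trivial gap. The calculation is a two-sample comparison of change scores, which is neither the ANOVA as worded nor the SAP model.

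**2. The literal wording.** One data set was simulated with 24 per arm, rho 0.6 and a true effect of −6.5. Regressing arm (0/1) on visit, SBP and their product gave coefficients 2.15, 0.0072 and −0.0167. These predict arm membership. None is a between-arm difference in mmHg.

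**3. Treatment read as a factor, on the same data.**

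| Analysis | Estimate (mmHg) | SE |
|---|---|---|
| Treatment-by-visit with a participant effect | −4.81 | 1.87 |
| Treatment-by-visit, rows independent | −4.81 | 3.46 (p = 0.17) |
| SAP 1.1 mixed model | −4.31 | 1.73 (p = 0.013) |

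This single data set is only an illustration that the unstated details can change the conclusion.

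**4. Precision in general.** With the change SD fixed at 8, the visit SD is s = 8 / √(2(1 − rho)). Then:
- change score: SE = 8 × √(2/24) = 2.31
- unpaired 2-way ANOVA: SE = s × √(4/24)
- SAP model: SE = s × √(1 − rho²) × √(2/24)
- power = Φ(6.5/SE − 1.96)

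| rho | s | Change score: SE, power | Unpaired ANOVA: SE, power | SAP model: SE, power |
|---|---|---|---|---|
| 0.3 | 6.76 | 2.31, 80% | 2.76, 65% | 1.86, 94% |
| 0.5 | 8.00 | 2.31, 80% | 3.27, 51% | 2.00, 90% |
| 0.8 | 12.65 | 2.31, 80% | 5.16, 24% | 2.19, 84% |

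**5. Within-arm tests.** Assume both arms fall by the same amount, with change SD 8 and 24 per arm. For a 3 mmHg fall, the standardised change is 3/8 = 0.375 and each arm is significant with probability about 0.42. Dapagliflozin alone is then significant with probability 0.42 × 0.58 = 0.24 (0.242 in 20,000 simulated trials). The simulated figure is 0.047 with no fall and 0.18 with a 4.6 mmHg fall.

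**6. Time points.** The protocol has one primary time point, week 12. The SAP's primary objective covers weeks 1 and 12, each at 5%, with no multiplicity rule. If the tests were independent, the chance of at least one false positive would be 1 − 0.95² = 9.75%. The tests share a baseline, so the true figure is probably somewhat lower.

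**The case against.** The SAP already gives a well-specified primary analysis, and it is normal for a SAP to refine a short protocol paragraph. A randomised arm cannot be an outcome, so *dependent* is almost certainly a slip. The primary outcome is worded as a reduction, and an ANOVA on change scores is already paired, with SE 2.31 and no power penalty. The ANOVA sentence also follows one on repeated measures and cites earlier work that may supply a participant term. The opening pages of the SAP are not in the available text and could contain a precedence statement.

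Most of this stands and limits the point. It does not make the sentence correct, and it does not reconcile two different methods in the current text.

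A reader might infer more than the documents support:
- *Following section 11 necessarily cuts power to a third or less.* That needs visits to be treated as unpaired and a correlation near the top of the assumed range. Section 11 does not require the unpaired analysis.
- *The ANOVA discards incomplete participants, contrary to ITT.* Section 11 gives no complete-case rule.
- *The within-arm ANOVAs are a rival primary test.* They are labelled as within-group comparisons, alongside the secondary outcomes.

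**Conclusion.** The point holds as an error of wording combined with an unreconciled change of method for the primary comparison. Taken literally, section 11 does not estimate its own primary outcome. With the likely slip corrected, it can target the same week-12 quantity as the SAP, but the standard error is left open: about 80% power on change scores, or 65% down to 24% if visits are unpaired. The last range rests on the assumed correlation of 0.3 to 0.8 and applies only to that reading.

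The sample size is not in question. With the protocol's SD of 8, the SAP week-12 model at 24 per arm has about 94% to 84% power over the same range. The 24% figure for the within-arm tests depends on an assumed common fall of 3 mmHg. It is a reason to label those results clearly, and it is not evidence that the plan would misuse them. The matter should be corrected before treatment codes are opened.

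**What to change.** In protocol section 11, replace the ANOVA sentences with the SAP 1.1 mixed model and name treatment as an explanatory factor. In both documents, name the week-12 treatment-by-visit estimate for seated SBP, with its 95% CI, as the single primary analysis, and move the week-1 model to secondary. Stating only that the SAP governs would not be enough, because it would bring in the SAP's two primary time points, each at 5%, in place of the protocol's one. Present within-arm changes as mean and 95% CI, labelled descriptive and not as evidence of a drug effect.

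The cost is a wording amendment to section 11 and a matching edit to the SAP's primary objective, primary outcome and section 1.1. No additional participants, visits or data are needed.

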5.3 Sample Size

The sample size is based on the primary endpoint of blood pressure. Currently, there is only one publication from our group with information available on the effect of SGLT2i on blood pressure reduction in KTR with diabetes. In this observational study of 10 KTR and simultaneous pancreas-kidney transplant recipients treated with canagliflozin, we reported a SBP decrease of $6.5 \pm 10 \text{ mmHg}^{63}$. Given the small sample size in our observational study, we believe the standard deviation would be smaller in a larger cohort. Blood pressure reduction with SGLT2 inhibition appear to be similar between patients with and without diabetes in non-transplant studies. We, therefore, estimated the sample size based on a SBP change of 6.5 mmHg with a standard deviation of 8 mmHg. Under the hypothesis that SGLT2i decreases SBP by $6.5 \pm 8 \text{ mmHg}$ compared to placebo with a two-sided alpha of 0.05 and 80% power, we calculate a sample size of n=48, with 24 randomized to dapagliflozin and 24 randomized to placebo. Assuming a 10% attrition rate, the final sample size required is 52 participants. This sample size is similar to those successfully used in previous studies⁷¹, and sufficient to measure secondary renal endpoints related to renal hemodynamic function⁷¹, natriuresis and arterial stiffness⁷²⁻⁷⁴. Based on previous studies, we anticipate an even sex distribution in each group.

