6. TREATMENT OF SUBJECTS

6.1 Investigational Product/Treatment

Dapagliflozin and matching placebo will be provided in 35 cc bottles, and the sponsor will be responsible for labelling. Each bottle of IP will be identified with a unique Composite ID in order to maintain the blind. By way of an Unblinding List, Pharmacy will provide treatment allocations of each Composite ID. The Unblinding List will be maintained within a secure location in the Pharmacy. Blinded personnel will not have access to this list. The blind must not be broken during the course of the study unless breaking the blind is required to provide medical care to the subject in the event of a medical emergency. The decision to break the blind is the responsibility of the Investigator. The Investigator may obtain treatment assignment directly from the unblinded Pharmacist. The Unblinding List will be used to confirm treatment assignment in the event of a medical emergency. Patients will take 10 mg dapagliflozin (1 tablet 10 mg once daily) or matching placebo according to randomised treatment scheme.

Study participants will be allocated to receive either 10 mg daily of dapagliflozin or a matching placebo for 12 weeks in a 1:1 ratio. Participants with diabetes will continue on existing medical therapy for glycemic control as recommended by Diabetes Canada⁷⁵. The study design is shown in **Figure 3.** The study investigator can titrate dapagliflozin down to 5 mg in the event that dapagliflozin 10 mg dose is not well tolerated by the participant. However, in the event of hypoglycemia, a decrease in dose of other glucose lowering therapies (including insulin), will be first initiated, if applicable, by the study investigator prior to down-titration of dapagliflozin. Every effort will be made to keep the dose of dapagliflozin constant at 10mg daily.

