## 4. Exploratory subgroup analyses

- 4.1. Compare diabetes vs non-diabetes status groups separately, and include test of interaction
  - a. Primary objectives
  - b. Secondary objectives
  - c. Exploratory objectives

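### Subgroup differences by sex/gender, measured GFR and T2D versus PTDM are to be sought by stratified analysis, and neither document specifies a treatment-by-subgroup interaction for these factors

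*Protocol*

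**What the plan says.** Protocol Section 11 joins an aim to a method for sex and gender: "However, data analyses will be stratified by sex and gender to detect any similarities or differences". It continues: "Other exploratory analyses will include stratification by GFR", with measured iohexol GFR below 45 set against above 45 mL/min/1.73 m², and it adds diabetes type (T2D and PTDM). No treatment-by-subgroup term is named. The same section says that the trial lacks the power to find differences by sex or gender. It calls those analyses exploratory and hypothesis generating, and says they may help in designing later studies.

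The SAP carries one subgroup factor, diabetes status. Its outcomes section says "Compare diabetes vs non-diabetes status groups separately, and include test of interaction". Its analysis section 4 adds to model 1.1 a main effect of diabetes status and a three-way term with time and treatment. Sex, gender, GFR and T2D versus PTDM do not appear there as subgroups.

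**The concern.** An analysis within each stratum asks whether dapagliflozin differs from placebo in that stratum. It does not ask whether the effect differs between strata. With about half the patients in each stratum, one stratum can reach significance and the other miss it purely by chance, although the true effect is the same in both.

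What is at stake is a false lead. A statement that pressure fell in one sex only, or only on one side of GFR 45, could be carried into later studies, which is the use the protocol has in mind. The GFR cut adds a second weakness: it turns a continuous baseline measurement into two groups and so discards information. As written, a value of exactly 45 belongs to neither group.

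**Working it through.** **Inputs.** Protocol Section 5.3: "based on a SBP change of 6.5 mmHg with a standard deviation of 8 mmHg"; "with a two-sided alpha of 0.05 and 80% power, we calculate a sample size of n=48". Each arm therefore has 24. The same section anticipates an even sex split in each arm, which gives 12 per arm per stratum. SD 8 is taken as the SD of the SBP change. The GFR split is not given and is varied below.

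**1. The plan's own figure.** n per arm = 2 × (1.96 + 0.8416)² × 8² / 6.5² = 23.8, rounded up to 24, so 48 in total. This reproduces the plan. Power at 24 per arm is 80.4% by the normal formula and 78.7% by the noncentral t.

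**2. Power within one stratum.** SE = 8 × √(2/12) = 3.27 mmHg and 6.5/3.27 = 1.99. Noncentral t power on 22 df is 47.7% (51.2% by the normal formula).

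**3. Patterns under an identical true effect, if each stratum is read at p<0.05.**
- Exactly one significant: 2 × 0.477 × 0.523 = 49.9%, that is about 25% for each named stratum.
- Both: 0.477² = 22.8%.
- Neither: about 27.3%.

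A simulation of 100,000 trials gave 50.1%, 22.8% and 27.2%. With 26 per arm (the full 52), exactly one is significant in 50.0%.

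**4. Sensitivity of the one-stratum figure** (24 per arm, noncentral t).

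| Setting | Exactly one significant |
|---|---|
| 40:60 split | 51% |
| 25:75 split | 58% |
| 20:80 split | 61% |
| Even split, SD 10 (pilot, Section 5.3) | 44% |
| Even split, SD 10.8 (pilot, Section 2.5) | 41% |
| Even split, SD 8, true effect 4 mmHg | 34% |
| Even split, SD 8, true effect 3 mmHg | 24% |
| T2D vs PTDM, about 7–10 vs 6 per arm | 40–44% |

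The last row assumes the population shares in Section 4 (T2D 30–40%, PTDM 25%); the trial's own shares are not given.

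**5. Interaction test, even split.**
- SE of the difference between two stratum effects = 8 × √(2/12 + 2/12) = 4.62 mmHg.
- 95% CI half-width = 1.96 × 4.62 = 9.1 mmHg.
- Simulated false-positive rate under a uniform effect: 5.1%.
- Power for a 6.5 mmHg difference between strata: Φ(6.5/4.62 − 1.96) = 29%.
- Difference detectable with 80% power: 2.80 × 4.62 = 12.9 mmHg.

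**6. Cutting GFR.** For a normally distributed moderator, the share of information kept by a cut with proportion p below it is φ(z)²/(p(1 − p)). This is 0.64 at p = 0.5, 0.58 at p = 0.3 and 0.49 at p = 0.2.

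The gain in power depends on a slope that neither document gives. Simulations assumed measured GFR with mean 55, SD 15 and minimum 30. Interaction power, continuous versus cut at 45, was about 59% versus 30% if the effect changes 0.4 mmHg per mL/min, 20% versus 11% at 0.2, and 9% versus 7% at 0.1.

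**The case against.** The strongest reply is that Section 11 sets no rule for comparing strata. A reader might infer that a difference will be declared when one stratum has p<0.05 and the other does not. The text does not say this, and it is also consistent with showing an estimate for each stratum. That stands: the 50% describes what such a reading would produce, not what the plan commits to. What remains is that the section gives detection of differences as the aim and offers no method that tests for one.

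Second, the protocol already calls these analyses exploratory and, for sex and gender, underpowered. That also stands and limits the consequences. It does not make separate analyses a test of difference.

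Third, the SAP does specify an interaction for the only subgroup it keeps, and the other analyses may never be run. That is fair, but the documents do not say that they were dropped, and diabetes yes/no does not answer the T2D versus PTDM question.

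Fourth, the case for continuous GFR can be overstated. The slope of 0.4 is assumed and steep: with 6.5 mmHg at GFR 55, it implies 6.5 − 0.4 × 25 = −3.5 mmHg at GFR 30, a rise in pressure. Protocol Section 7.3 expects blood pressure effects not to depend on GFR. At modest slopes power is poor either way.

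**Conclusion.** For sex/gender, measured GFR and T2D versus PTDM, the plan offers stratified analysis and no test of whether effects differ. The size is conditional. It rests on strata being read by p<0.05 and on a uniform true effect. On those terms a one-stratum result appears in about 50% of trials at the planning values with an even split, in 41–44% at the pilot SDs, and in 24–34% if the true effect is 3–4 mmHg. The interaction test errs in about 5%. The documents anticipate the even split for sex only.

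A reader might infer that a result in men only is the likeliest outcome under a uniform effect. It is not: neither stratum significant (27%) is more likely than either named stratum alone (25% each), and the 50% pools two opposite patterns. Nor does the interaction test make the trial informative about modest differences, since its power is about 29% for a 6.5 mmHg difference. Its gain is control of false differences and a visible statement of uncertainty. No primary conclusion is affected.

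**What to change.** In protocol Section 11 and SAP section 4, state for each factor whether it is kept. For each one kept:

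- Fit one model in all participants: SAP model 1.1 plus the subgroup main effect, subgroup-by-visit and treatment-by-visit-by-subgroup. SAP section 4 does not name subgroup-by-visit; without it, the placebo change is assumed equal across subgroups.
- For diabetes type, use three levels (none, T2D, PTDM) and report the T2D versus PTDM contrast.
- Report the interaction estimate with its 95% CI. Show stratum effects with CIs as description only, without within-stratum p-values.
- For GFR, base the interaction on continuous baseline (Visit 3) measured GFR, for example per 10 mL/min/1.73 m². If categories are also shown, assign the value 45 to one of them.

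If the SAP is meant to drop these subgroups, say so and bring Section 11 into line. The cost is wording and a few extra model fits, with no new data or patients. The price is that the imprecision, about ±9 mmHg for an even split and more for uneven ones, becomes visible in the report.

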9.2 Randomization, blinding and treatment allocation

The randomization scheme will be computer-generated by an independent biostatistician. To achieve a balance of participants in each arm, permuted block randomization will be used with variable blocks of 4 and 6. Randomization will be stratified based on T2D and PTDM status, as the effects of dapagliflozin may differ between these two groups. Participants will be randomized only after screening and informed consent has been obtained. All participants, nurses, physicians, study coordinators and investigators will be blinded to the treatment allocation. In addition, all participants, study personnel and study sponsor will be blinded until the end of the trial to all the laboratory and test results obtained during the trial. Dapagliflozin and placebo tablets, as well as drug packaging will be identical in appearance. Adherence to the intervention will be determined using pill counts and questioning of participants at each study visit⁸⁷. Reasons for non-adherence and drug discontinuation will be ascertained.

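### The protocol and SAP disagree on the planned subgroup analyses: sex and gender, measured GFR and diabetes type appear only in the protocol, and the SAP gives no reason

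*Protocol*

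**What the plan says.** **Protocol section 11** commits to three sets of exploratory analyses.

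- Sex and gender: "data analyses will be stratified by sex and gender to detect any similarities or differences". The same paragraph concedes: "This clinical trial is not sufficiently powered to detect sex- or gender-based differences".
- Measured GFR and diabetes type: "Other exploratory analyses will include stratification by GFR (measured iohexol GFR of <45 ml/min/1.73m² vs. >45 ml/min/1.73m²), as well as diabetes type", with T2D and PTDM given as the types.

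**Protocol section 9.2** describes the allocation: "Randomization will be stratified based on T2D and PTDM status, as the effects of dapagliflozin may differ between these two groups". It does not list the strata, and the trial also enrols recipients with neither condition.

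**SAP section 4** (under Objectives, Outcomes and the analysis text) has a single factor: "Compare diabetes vs non-diabetes status groups separately, and include test of interaction". Its model adds to the primary mixed model a diabetes main effect and a three-way term of diabetes, time and treatment.

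Elsewhere in the SAP, sex is only a baseline-table variable (item 0 of the analysis text). GFR is a baseline descriptor (as eGFR), an outcome (2.7) or a variable in the association models (3.3 and 3.5). It is never a modifier of the treatment effect. T2D and PTDM are nowhere separated.

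**The concern.** The SAP is not a short document confined to the primary analysis. It lists eight exploratory objectives, a subgroup section with an interaction test, and a further section of additional analyses. The three protocol-named modifiers are missing from this long list without comment. An analyst following the SAP would not run them, and an analyst following the protocol would.

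At stake is the clarity of pre-specification. If results by sex, GFR or diabetes type are published, a reader comparing them with the SAP alone may take them for data-driven choices. If they are not published, a protocol commitment has lapsed with no record of the decision.

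The GFR item bears on the trial's rationale. Protocol sections 2.3, 2.5 and 7.3 argue from earlier evidence that blood pressure lowering holds up as kidney function falls while glucose lowering weakens. Measured GFR is obtained at week 0 (section 9.3), so the data will exist.

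**Working it through.** **1. The texts side by side**

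| Modifier | Protocol section 11 | SAP section 4 |
|---|---|---|
| Sex and gender | planned, exploratory | absent |
| Measured iohexol GFR, cut at 45 | planned, exploratory | absent |
| T2D and PTDM | planned, exploratory | absent; the two are merged |
| Diabetes yes/no | not listed | planned, with interaction test |

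**2. Does the SAP factor match the randomisation factor?** If the strata are diabetes yes/no, it matches. If they are T2D, PTDM and neither, the SAP covers the factor only in part. Section 9.2 speaks of two groups whose effects may differ, and section 11 speaks of diabetes type; both lean towards the second reading. Neither settles it.

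**3. The plan's own figure.** Inputs from protocol section 5.3: difference 6.5 mmHg, SD 8 mmHg, two-sided alpha 0.05, power 80%, 1:1 allocation.

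n per arm = 2 × (1.960 + 0.842)² × 8² / 6.5² = 23.8, rounded up to 24, or 48 in total. This reproduces the stated number.

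**4. Precision of the missing analyses.** These figures use the same SD and 48 evaluable participants, and treat the analysis as a comparison of changes.

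- Overall treatment effect: SE = 8 × √(2/24) = 2.31 mmHg.
- Sex, split evenly as section 5.3 anticipates (12 per arm per sex): interaction SE = 8 × √(4/12) = 4.62 mmHg. The 95% half-width is 1.96 × 4.62 = 9.1 mmHg. The interaction detectable with 80% power is 2.80 × 4.62 = 12.9 mmHg, and power for an interaction of 6.5 mmHg is about 29%.
- GFR split at 45. The share below 45 is not given; I assume 20% to 50%. At 50% the SE is again 4.62. At 20% (4.8 and 19.2 per arm) it is 8 × √(2/4.8 + 2/19.2) = 5.77 mmHg. Detectable interaction: 12.9 to 16.2 mmHg.
- T2D versus PTDM. The numbers are not given; I assume 4 to 8 per arm in each type. SE = 8 × √(4/8) = 5.66 to 8 × √(4/4) = 8.0 mmHg. Detectable difference: 15.8 to 22.4 mmHg; power for 6.5 mmHg: about 21% down to 13%.

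**5. The existing diabetes model.** The terms named in the SAP are visit, treatment-by-visit, diabetes, and diabetes-by-visit-by-treatment. Diabetes-by-visit is not named. Without it, the model gives diabetic and non-diabetic placebo participants the same change over time. If their changes in fact differ, part of that difference is absorbed into the three-way term and looks like a treatment interaction. The wording may be shorthand for a full factorial, but it does not say so.

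**The case against.** The strongest reply is that nothing has been withdrawn. Protocol section 11 still stands, the SAP does not revoke it, and an analysis by sex, GFR or diabetes type can be reported as planned by citing the protocol. This is correct. A reader might infer that these questions can no longer be answered, or that any later answer is necessarily post hoc. The documents show only an unexplained discrepancy.

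Second, the diabetes yes/no contrast is not an arbitrary substitute. Anticipated outcome 4 in protocol section 3.3 expects modest glucose lowering in recipients with T2D or PTDM and none in those with neither. The SAP factor serves that hypothesis. This stands, and the contrast should be kept.

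Third, a reader might infer that the SAP ignores the factor used in randomisation. Because the strata are not listed, that is not established.

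Fourth, no objective or anticipated outcome asks whether the blood pressure effect varies with baseline GFR. Omitting the GFR analysis loses a planned exploratory item that the rationale makes interesting, not the test of a stated objective. That also stands. The unassigned value of exactly 45 is trivial for a continuous measurement.

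Lastly, the analyses are exploratory and weak, as the protocol itself says for sex and gender. This limits what they can show. It does not explain why one document lists them and the other does not.

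**Conclusion.** The point holds as a conflict between the two documents on exploratory analyses. All three modifier analyses in protocol section 11 are absent from SAP section 4, with no reason given. The primary estimate, its test and the sample size are untouched.

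The figure of 4.6 mmHg, twice the overall standard error, applies only to two equal subgroups that together make up the whole sample. Protocol section 5.3 supports that for sex alone. For T2D versus PTDM, which leaves out recipients without diabetes, about 6 to 8 mmHg is more realistic under the assumed 4 to 8 per arm. All these figures rest on the protocol's SD of 8 mmHg and would widen in proportion to a larger SD. The results could therefore be read only as estimates with wide intervals, not as tests.

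**What to change.** Before unblinding:

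1. State the randomisation strata explicitly.
2. Keep the diabetes yes/no analysis and add diabetes-by-visit to its model.
3. Add to SAP section 4, for seated SBP and at most a short named list of other outcomes, effect-modifier analyses by:
   - sex and gender;
   - baseline (Visit 3) measured GFR as a continuous modifier, with <45 versus ≥45 for display only;
   - T2D, PTDM and no diabetes.
4. In each model include the modifier main effect, modifier-by-visit, and modifier-by-visit-by-treatment. Report estimates with 95% confidence intervals, labelled hypothesis-generating.
5. Alternatively, for any of these analyses that is not wanted, record the removal and the reason.

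The cost is a paragraph in the SAP, with no new data and no change in sample size. The downside is more imprecise estimates. For seated SBP alone, one term each for sex, gender (if two levels) and GFR, plus two diabetes contrasts, over the acute and chronic windows gives 5 × 2 = 10 interaction terms. The count grows with every added outcome, so the list should stay short.
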